5.2 Informed Consent

Objective 1: A waiver of informed consent will be used for the randomized pilot trial. A waiver of informed consent is advocated for certain pragmatic trials testing methods for comparing and improving the delivery of established interventions within health care systems. The present study meets criteria for such an alteration of the requirement for informed consent set forth in the Common Rule in the following ways:

- The research involves no more than minimal risk to subjects. The risks to subjects participating in this study and interventions are aimed at improving patient knowledge

and completion of molecular testing. In Sections 7.1 and 7.3, we outline the safeguards we have in place to prevent any breach of confidentiality – the primary risk of study participation.

- The waiver or alteration will not adversely affect the rights and welfare of the subjects.
- To the extent possible, the subjects will be provided with pertinent information after participating in the trial.
- The research cannot be practicably conducted without a waiver or alteration of the requirement for informed consent. This is an explicitly pragmatic approach designed to test the real-world effectiveness of an early telehealth nurse navigation visit to provide patient education and coordinate molecular testing. Key outcomes include assessment of patient centered communication and patient and clinician satisfaction. Requiring traditional (opt-in or opt-out) individual consent would introduce important selection biases (e.g., trial patients would be those willing to be randomized to receipt of a telehealth visit). Knowledge of the trial arms would bias participant opinions on the education and care coordination interventions and influence their views on satisfaction with care received. This would impact the value of the knowledge to be obtained because it would not generalize to the full range of patients diagnosed with lung cancer.

All participants will retain the right to decline patient education or plasma-based molecular testing or other ordered studies, regardless of study assignment.

Objective 2: Potential interview participants will be initially contacted by study team members by email or letter and given the option to decline further contact from the team. If the participant has not opted out within two weeks, they will be contacted by phone to assess their interest in participating in the study. If the participant agrees to participate, they will be scheduled to have an interview in-person, by phone, or using a HIPAA-compliant video platform (based on preference and study procedures at the time). For this portion of the study, a waiver of documentation of written informed consent will be used because the risk to the individual is minimal, a signed informed consent form (ICF) could identify that an individual participated in the study, and obtaining a signed paper form would significantly decrease the likelihood of proceeding towards an interview. Prior to the start of the interview, research staff will review the study purpose, procedures, and the rights of the participant. They will also provide an information statement to participants via email prior to the scheduled interview. Research staff will state that participation is voluntary and ask for the participant's permission to record their interview. They will describe the transcription and de-identification process, and they will ask permission to proceed with the interview. All participants will be free to withdraw participation at any time, and study enrollment will not impact employment or care at Penn Medicine.

5.3 Compensation

Objective 1: Patients who participate in the randomized clinical trial (Objective 1) will not receive compensation.

Objective 2: All patients and clinicians who complete the semi-structured interviews and surveys will receive \$50 for their participation. Payments will be made through issuance of GreenPhire ClinCards, which can be used in the same manner as a debit card. The ClinCards will be mailed to participants within 10 days after interview and survey completion.

5.4 Measures and Endpoints

Objective 1: The specific outcomes align with 5 key endpoints (access, quality, outcomes, equity, and efficiency). The primary endpoint is receipt of a molecularly-informed treatment recommendation at the time of the patient's initial in-person oncology visit, measured up to 12 weeks from randomization. This outcome encompasses successful completion of comprehensive molecular testing and the ability of the patient and oncology care team to have all necessary information to collaboratively arrive at the optimal treatment approach. We anticipate that approximately 10% of patients randomized to usual care will be able to receive a molecularly-informed treatment recommendation at initial visit – these include patients in whom tissue was successfully tested and identified a targetable mutation prior to referral. We anticipate this will be substantially improved with enhanced nurse navigation (See Section 6.1 Sample Size). The primary endpoint will be assessed by review of clinician documentation (e.g., progress notes) within the electronic medical record (EMR) on the day of the initial visit.

Secondary outcomes include:

- 1) Operational endpoints:
 - a. Rate of completion of telehealth visit defined as successful completion of a nurse navigator telehealth visit prior to biopsy, measured up to 3 weeks from randomization.
 - b. Rate of completion of comprehensive molecular testing (tissue and/or plasma testing) prior to initiation of first line therapy, measured up to 12 weeks from randomization.
- 2) Clinical endpoints:
 - a. Time from randomization to molecularly-informed treatment recommendation, measured up to 12 weeks from randomization.
 - b. Proportion of participants with one or more targetable mutations, measured up to 12 weeks from randomization.
 - c. Overall survival, measured as 1-year overall survival from time of randomization to death from any cause.
 - d. The proportion of enrolled patients with a diagnosis other than metastatic NSq NSCLC (telehealth arm only), measured at 12 weeks from randomization.
 - e. Time from randomization to treatment initiation, measured up to 12 weeks from randomization.
- 3) Cost outcomes:
 - a. Intervention costs (measured using a pragmatic method to capture and analyze all system-level resources, such as personnel time and patient outreach costs) that are needed to deploy telehealth strategies in routine care.¹⁹

Objective 2: We will use structured and validated measures and a semi-structured interview guide based on our Framework for Integrating Telehealth Equity (FITE) to systematically evaluate individual and contextual factors (e.g., treatment knowledge, medical mistrust, clinical beliefs, patient-centered communication, financial toxicity, and knowledge of genetic testing) that will shape the effectiveness of telehealth strategies. Domains that will be assessed as part of the Objective 2 include:

- 1) Telehealth usability, acceptance, and satisfaction (using the University of Pittsburgh Telehealth Usability Questionnaire)
- 2) Patient-centered communication (using the University of North Carolina Patient-Centered Communication in Cancer Care Instrument)
- 3) Medical-related trust and mistrust (using the Group-Based Medical Mistrust Scale [GBMMS])
- 4) Acceptability, appropriateness, and feasibility of interventions (using the Acceptability of Intervention Measure [AIM] Intervention Appropriateness Measure [IAM] and Feasibility of Intervention Measure ([FIM]))
- 5) Treatment related knowledge and beliefs
- 6) Other contextual factors (e.g., organizational climate, barriers to using telehealth) that may impact effectiveness of trial

Objective 2 endpoints for the subset of enrolled participants will be assessed up to 1 year from randomization.

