4.2 Overview

Prior to the trial launch, we will use a rapid-cycle approach (RCA) to optimize delivery of the enhanced synchronous telehealth nurse navigation visit and coordination/default ordering of molecular testing. RCA procedures will involve design meetings with the study team, discussions with administrators and clinicians who are members of our Implementation Lab, as well as contextual inquiry with clinicians and patients to elicit feedback.

Objective 1: As shown in **Figure 1**, this two-arm pilot trial will randomize patients with suspected locally advanced/metastatic NSCLC who are scheduled for an appointment in the lung cancer evaluation clinic. Eligible patients will be identified by screening of clinical schedules by study staff using the EMR. Prior to or soon after completing an appointment in the lung cancer evaluation clinic, eligible patients will be randomized to either enhanced synchronous telehealth nurse navigation or to usual care nurse navigation.

Usual Care Arm:

Currently, in the standard care pathway at Penn Medicine, a patient who is being evaluated for lung cancer has an appointment within the lung cancer evaluation clinic and is then scheduled for a biopsy (e.g., bronchoscopy, transthoracic needle biopsy). After the biopsy is complete, the patient's clinician contacts the trained lung cancer nurse navigator, who then calls the patient to 1) review the roles of clinicians on the medical oncology care team; 2) provide brief education on lung cancer; and 3) review the patient's diagnostic history and coordinate collection or completion of imaging required for guideline-recommended cancer staging. In the standard care pathway at Penn Medicine this phone call between the patient and the lung cancer nurse navigator usually takes place after the biopsy is complete, though there are some cases in which the clinician asks the lung cancer nurse navigator to reach out to the patient sooner.

For patients randomized to the usual care arm of this study, the researchers will ask the clinicians and the lung cancer nurse navigator not to arrange plasma-based testing earlier than the date of the initial in-person medical oncology visit. Instead, the lung cancer nurse navigator can have the patient complete a blood draw for plasma-based testing on the same day as their initial in-person medical oncology visit.

Intervention (Telehealth) Arm:

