Patients in the intervention arm will be scheduled for an enhanced synchronous telehealth visit with a trained lung cancer nurse navigator prior to tissue biopsy. The enhanced synchronous telehealth visit will ideally occur between the initial clinical appointment and diagnostic biopsy (typically a period between two and seven days). In addition to the activities conducted as part of usual care, the nurse navigator will: 1) provide more detailed and individualized education on lung cancer and the rationale for comprehensive molecular testing, including plasma-based tests; and 2) if the patient agrees to testing, pend a default order for plasma-based molecular testing (if not already ordered) for the clinician to sign and arrange for phlebotomy to be performed during the periprocedural window associated with the patient's tissue biopsy.

Objective 2: Using rigorous approaches proven successful in our prior work,^{15,16} we will recruit 20-30 patient participants of the primary trial and 10-15 clinicians and clinical leaders to complete semi-structured interviews following the active trial period.

Patients: We will oversample for Black patients to understand effectiveness by race/ethnicity and stratify by trial outcome and study arm to understand factors contributing to both success and failure (e.g., primary endpoint) in either group (5-10 patient in each stratum). Trial participants will be invited in randomly selected batches each month (to enhance capture over time) until we reach our target sample of approximately 20-30 patients. Patients will be invited to participate in interviews via email and/or letter within 6 weeks of their in-person oncology visit.

Clinicians: Recruitment for clinicians will be similar to the procedure for patients, except we will wait until the completion of the full trial to conduct interviews to avoid potential contamination. Clinicians will be purposively sampled by clinical role (e.g., oncologists, nurses, clinical leads) to enhance variation and invited via email. Recruitment will continue until we reach our target sample of 10-15 clinicians.

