5.5 Sources of Materials

Objective 1: Electronic health record (EHR) data will be used to collect the primary endpoint as well as covariates required for statistical analysis. We will use the EHR and survey data collected to assess secondary endpoints.

Objective 2: Semi-structured interviews will be collected and analyzed in conjunction with quantitative measures conducted as part of the RCT.

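### The primary endpoint is scored from clinician notes alone, with no required check that a molecular result was available by the visit and no concealment of arm from the reader

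*Combined protocol and SAP*

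**What the plan says.** Section 5.4 gives the only ascertainment rule for the Objective 1 primary endpoint: it is "assessed by review of clinician documentation (e.g., progress notes) within the electronic medical record (EMR) on the day of the initial visit". Section 5.5 adds "Electronic health record (EHR) data will be used to collect the primary endpoint" and names no field or document.

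On content, 5.4 states: "This outcome encompasses successful completion of comprehensive molecular testing". It also says that the patient and team should have the information they need to choose treatment. Its example of a usual-care success is a patient in whom "tissue was successfully tested and identified a targetable mutation prior to referral".

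On who knows the arm, section 4.2 (Usual Care Arm) says "the researchers will ask the clinicians and the lung cancer nurse navigator not to arrange plasma-based testing earlier", the cut-off being the day of the first oncology visit. In the telehealth arm the navigator explains molecular testing and, if the patient agrees, will "pend a default order for plasma-based molecular testing" for the clinician to sign.

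On checking, section 4.3 mentions verification of endpoints and section 7.1 mentions verification of entered data, both in general terms. The only masking described is of participant identity for Objective 2 confidentiality (7.3). Section 5.2 recognises that knowing the arm can bias participants' opinions, but does not extend this to note writers or chart readers.

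**The concern.** The words about the day of the visit date the documentation, not the molecular result. The plan does not tell an abstractor to find a report and compare its date with the visit. It does not say whether a negative result that leads to a recommendation counts: the usual-care example in 5.4 is an identified targetable mutation. Section 4.1 cites a 47% historical rate of treatment recommendation against the 10% expected in 5.4, without saying whether the two use the same definition. Borderline charts are therefore left to the reader's judgement.

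That judgement may differ by arm. Telehealth-arm charts will tend to say more about molecular testing because of the navigator visit and the plasma order, and a reader with the whole record can see this. Clinicians and the navigator act on arm-specific requests, and the oncologist who writes the note may infer the arm from the chart. With few events expected in the control arm, a handful of charts read generously in one arm could move the primary result. Section 6.1 says the results will inform later studies, so an inflated signal would carry forward.

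**Working it through.** **Inputs.** From 6.1: 10% in usual care, a 20-point absolute increase, a two-sided test, 124 participants (62 per arm) and 138 after dropout (69 per arm). From 6.2.1: ITT, unadjusted logistic regression. Assumed, because the documents do not give them: alpha 0.05 and a misreading share f.

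**The plan's own figure.** n per arm = [1.96 × √(2 × 0.20 × 0.80) + 0.8416 × √(0.10 × 0.90 + 0.30 × 0.70)]² / 0.20² = (1.109 + 0.461)² / 0.04 = 61.6, so 62 per arm and 124 in total. Power at 62 per arm is 80.3%. 124 / 0.90 = 137.8, so 138. The plan's figures reproduce.

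**One-sided misreading, no true effect.** Let both true rates be 10%, and let a share f of true failures be read as successes in the telehealth arm only. The observed telehealth rate is 0.10 + 0.90f. True failures in that arm number 0.90 × 62 = 55.8 or 0.90 × 69 = 62.1, so f = 5% is about 3 patients and f = 10% about 6. The table gives the exact binomial probability of a significant result favouring telehealth, at 62 / 69 per arm.

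| f | Observed telehealth rate | Uncorrected chi-square | Wald test of log odds ratio |
|---|---|---|---|
| 0 | 10.0% | 2.5% / 2.6% | 1.5% / 1.6% |
| 2% | 11.8% | 5.0% / 5.2% | 3.6% / 3.8% |
| 5% | 14.5% | 11.1% / 12.1% | 9.4% / 10.0% |
| 10% | 19.0% | 28.7% / 32.1% | 27.4% / 29.1% |
| 15% | 23.5% | 52.0% / 57.5% | 51.4% / 54.7% |

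For scale, with 7 events among 69 controls, 16 telehealth events reach p<0.05, an excess of 9.

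**Same misreading, a real but smaller effect.** With true rates of 10% and 20%, the observed telehealth rate is 0.20 + 0.80f: 24% at f = 5% and 28% at f = 10%. The apparent difference grows from 10 points to 14 or 18. The chance of p<0.05 rises from 33.6% / 37.6% to 54.6% / 60.2% and then 73.5% / 78.9%.

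**Equal misreading in both arms (62 per arm).** Type I error stays at 4.7% for f = 5% or 10%. Exact power for 10% against 30% falls from 81% to 71% (f = 5%) or 61% (f = 10%).

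**The case against.** A reader might infer that a note mentioning only a pending plasma test counts as a success under the protocol. It does not: 5.4 ties the outcome to completed testing, so scoring such a note as a success would be an abstraction error. What stands is that no step is laid down to catch the error.

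A reader might also infer that the oncologists who write the endpoint notes are told the allocation. Section 4.2 does not say so. The clinician described there is the one who contacts the navigator after biopsy, before the oncology visit. The oncologist may work out the arm from the chart, which is a weaker claim.

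The strongest objection is to the size. No misreading rate is documented; error in one arm and one direction is an assumption; and a true effect of zero is not the likeliest case, since the design brings plasma testing forward in one arm and holds it back in the other. This is accepted. The figures show sensitivity and are not a forecast. The calculation with a real effect shows that the concern does not depend on a null effect, and equal error costs power instead.

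Masking has a limit too. Because usual-care plasma testing is held until the visit date, a plasma report dated before the visit largely identifies the telehealth arm, so a reader given that report is not masked. A rule relying only on in-system dates could also wrongly fail usual-care patients whose tissue was tested before referral. Both limits shape the fix.

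Finally, an abstraction form may exist in a manual outside these documents. If so, its key rules belong in 5.4.

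**Conclusion.** The concern holds as a weakness in how the endpoint is ascertained. The concept in 5.4 is sound, but scoring rests on notes read without a required result date and without concealment of arm. Under the stated assumptions (alpha 0.05, 10% true rate in both arms, misreading in the telehealth arm only), about three misread charts raise the chance of a falsely favourable result from about 2.5% to 11-12%, and about six raise it to 29-32%. The Wald test, which is closer to the planned logistic model, gives 9-10% and 27-29%. The documents do not show that misreading will occur or in which direction, and it would be wrong to read these figures as the trial's actual error rate. The change is worth making before charts are abstracted because it is cheap and protects the sole primary endpoint of Objective 1.

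**What to change.** In section 5.4, score success only if both items hold:

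- **(a)** a final tissue or plasma molecular report, internal or outside, carries a report date on or before the initial oncology visit. This is extracted separately as an objective item.
- **(b)** the note for that visit documents a treatment recommendation that uses that result.

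State whether a negative result that leads to a recommendation counts.

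Existing study staff who took no part in randomisation or navigation should judge (b) on a fixed form from the oncology note alone, without the allocation, the navigator notes or the plasma report. Items (a) and (b) are combined afterwards.

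The cost is protocol wording, a one-page form and some effort to find the dates of outside reports. The sample size stays at 124 evaluable and 138 randomised. Some notes will still reveal the arm, so masking is partial and the dated report carries most of the protection.

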5.5 Sources of Materials

Objective 1: Electronic health record (EHR) data will be used to collect the primary endpoint as well as covariates required for statistical analysis. We will use the EHR and survey data collected to assess secondary endpoints.

Objective 2: Semi-structured interviews will be collected and analyzed in conjunction with quantitative measures conducted as part of the RCT.

6. STATISTICAL DESIGN AND POWER

6.1 Sample Size

Objective 1: Sample size is based on estimates of receiving a molecularly-informed treatment recommendation at the initial oncology visit. Based on our prior studies, we anticipate this will occur in 10% of patients in the usual care arm. This pilot study is designed to detect an absolute increase of 20% in our primary outcome for patients in the intervention arm. With a sample size of 124 participants and a two-sided alpha, we will have >80% power to detect an increase of this magnitude. Given the potential for drop-out of patients following randomization, we have increased the estimate by 10%, leading to a final sample size of 138 participants (69 in each arm). Although a difference <20% in our primary outcome rate may be clinically meaningful, this sample size is an optimal balance to allow an assessment of our primary and secondary outcomes and assess for mechanisms of action. Study outcomes will be used to preliminarily assess effectiveness across all outcome domains to inform the design of future studies, including a pragmatic trial, if warranted.

Objective 2: Proposed sample size is based on the estimated number of interviews needed to reach data saturation within each group and by intervention outcome to support mixed methods evaluation; however, interviews will continue until saturation is achieved.^{16,21}

6.2 Analysis Plan

6.2.1 Objective 1 Primary Analyses

We will produce data summaries to assess data quality and demographic and clinical characteristics across arms. First, our primary analytic approach will be to conduct ITT analyses

using unadjusted logistic regression to compare the overall effectiveness of the intervention to result in receipt of a treatment recommendation at the initial in-person visit and time to treatment initiation. The ITT analysis provides an unbiased test of the overall effectiveness of the interventions. An additional analysis will adjust for imbalanced covariates, where imbalance is determined by standardized mean differences >0.1 . If the number of imbalanced covariates exceeds the number allowed for adjustment based on the number of events, we will prioritize covariates with the largest imbalances.

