2.3 Secondary Outcomes

Objective 1: Secondary outcomes include:

- 1) Rate of telehealth visit completion
- 2) Rate of completion of comprehensive molecular testing (tissue and/or plasma testing) prior to initiation of first line therapy
- 3) Identification of one or more targetable mutations
- 4) Timeliness of molecularly-informed treatment recommendation
- 5) Overall survival
- 6) Intervention costs
- 7) Proportion of patients with diagnosis other than metastatic NSq NSCLC (telehealth arm only)
- 8) Time to treatment initiation

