6.2.2 Objective 1 Secondary Analyses

We will use regression methods to assess the impact of the telehealth intervention on secondary outcomes of telehealth visit completion, rate of comprehensive molecular testing, patient satisfaction, clinician acceptability, and intervention costs, with logistic, Cox proportional hazards, and linear regression for binary, time-to-event, and continuous outcomes, respectively. Additional secondary analyses will adjust for factors that exhibit residual imbalance between randomized intervention groups. In addition, secondary as-treated analyses will be conducted.

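### Section 6.2.1 puts time to treatment initiation, a secondary time-to-event outcome, under logistic regression in the primary analysis

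*Combined protocol and SAP*

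**What the plan says.** The analysis section and the outcome sections treat time to treatment initiation differently.

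- **6.2.1, primary analyses.** The approach is intention-to-treat, "using unadjusted logistic regression to compare the overall effectiveness of the intervention", applied to "receipt of a treatment recommendation at the initial in-person visit and time to treatment initiation". No cut-off, censoring rule or error allocation is given for the second outcome.
- **2.2 and 5.4.** Each names one primary outcome for Objective 1, and it is binary: a molecularly-informed recommendation at the first oncology visit.
- **2.3.** The list of secondary outcomes ends with "8) Time to treatment initiation". The Protocol Summary has the same list.
- **5.4.** Among the secondary clinical endpoints it is defined as "Time from randomization to treatment initiation, measured up to 12 weeks from randomization".
- **6.2.2, secondary analyses.** The methods are "logistic, Cox proportional hazards, and linear regression for binary, time-to-event, and continuous outcomes, respectively". The outcomes named are "secondary outcomes of telehealth visit completion, rate of comprehensive molecular testing, patient satisfaction, clinician acceptability, and intervention costs". Time to treatment initiation is not among them.
- **6.1.** "Sample size is based on estimates of receiving a molecularly-informed treatment recommendation at the initial oncology visit". No effect size, event count or power is given for time to treatment initiation.

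**The concern.** There are two conflicts. On status, 6.2.1 places in the primary analysis an outcome that every outcome list calls secondary. On method, it gives a time-to-event outcome a model for binary data, while 6.2.2 reserves Cox regression for outcomes of that type.

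The method conflict matters more. Earlier treatment is part of the central hypothesis in Section 1. A logistic model of having started by some week asks whether treatment began within the window. It does not ask whether treatment began sooner. Two arms in which nearly everyone starts by week 12 look almost alike to that model, even if one starts weeks earlier.

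Leaving both readings available also means that the model for this outcome could be settled after the data are seen.

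**Working it through.** **1. The plan's own figure.** Inputs from 6.1: 10% versus 30%, two-sided, power above 80%, 10% dropout. The alpha level is not stated, so 0.05 is assumed. With the pooled-variance formula and no continuity correction:

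n per arm = [1.960·√(2·0.20·0.80) + 0.842·√(0.10·0.90 + 0.30·0.70)]² / 0.20² = (1.109 + 0.461)² / 0.04 = 61.6, rounded up to 62.

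This gives 124 in total, and 124/0.90 = 137.8, or 138. Power is 80.3% at 62 per arm and 84.3% at 69 per arm. The stated figures reproduce. They rest on the binary endpoint alone, so moving the time outcome does not alter them.

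**2. Which method attaches to the time outcome.** Section 6.2.1 is the only analysis text that names it, and the method there is logistic regression. The Cox clause in 6.2.2 could reach it by outcome type only. None of the five outcomes listed in 6.2.2 is defined in 5.4 as a time to an event.

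**3. What the logistic reading costs.** The documents give no initiation rates, so these are assumptions: exponential times, censoring at 12 weeks, two-sided 0.05, no deaths or losses. The share started by 12 weeks is (1 − c)(1 − 2^(−12/m)), where m is the median among starters in weeks and c the share who never start. A value of c = 30% is included because eligibility rests on suspected disease and an intention-to-treat analysis keeps patients who turn out to have something else.

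The table gives power from 10,000 simulated trials per scenario. The log-rank test is the score test of a Cox model with arm only. The comparator is the Wald test from a logistic model of having started by 12 weeks.

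| Medians, usual care vs telehealth (weeks) | Never start | Started by week 12 | 69 per arm: log-rank vs logistic | 62 per arm: log-rank vs logistic |
|---|---|---|---|---|
| 4 vs 2.5 | 0% | 87.5% vs 96.4% | 75.7% vs 34.0% | 70.2% vs 26.9% |
| 5 vs 3 | 0% | 81.1% vs 93.8% | 80.6% vs 58.2% | 76.0% vs 52.7% |
| 6 vs 4 | 0% | 75.0% vs 87.5% | 56.8% vs 45.3% | 53.6% vs 42.6% |
| 12 vs 6 | 0% | 50.0% vs 75.0% | 88.9% vs 85.8% | 86.2% vs 83.8% |
| 4 vs 2.5 | 30% | 61.3% vs 67.5% | 20.4% vs 11.0% | 19.0% vs 10.9% |
| 5 vs 3 | 30% | 56.7% vs 65.6% | 27.9% vs 18.0% | 26.1% vs 17.9% |
| 6 vs 4 | 30% | 52.5% vs 61.3% | 22.5% vs 17.7% | 20.8% vs 18.0% |
| 12 vs 6 | 30% | 35.0% vs 52.5% | 59.3% vs 55.1% | 54.3% vs 52.7% |

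Logistic regression is weaker in all 16 comparisons. The smallest gap is 54.3 − 52.7 = 1.6 points and the largest 70.2 − 26.9 = 43.3 points.

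**4. Closed-form check of the first row, 69 per arm.** Expected events are 69·(0.875 + 0.964) = 126.9 and the hazard ratio is 4/2.5 = 1.6. Log-rank power is Φ(√126.9/2·ln 1.6 − 1.960) = Φ(0.69) = 75%, which agrees with the simulation.

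For the binary comparison, the pooled two-proportion formula with p̄ = 0.920 gives Φ[(0.0891·√69 − 1.960·√(2·0.920·0.080)) / √(0.875·0.125 + 0.964·0.036)] = Φ(−0.04), about 49%. The simulated Wald figure is lower, at 34%, because the Wald test is conservative when few patients are left unstarted. In this row, then, about 27 points of the loss (75 − 49) come from reducing a time to yes or no. The rest comes from the Wald test.

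**5. Error rate.** If success on either outcome counted, each tested at 0.05, the family-wise error would be 1 − 0.95² = 9.75% with independent tests, and about 7% with correlation 0.9. The documents state no such success rule, so this is conditional.

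**The case against.** The best reply is that this is a drafting slip with an obvious reading. Since none of the outcomes listed in 6.2.2 is a time to an event, its Cox clause has work to do only for the unlisted ones: time to recommendation, overall survival and time to treatment initiation. Status is also clear elsewhere, because 2.2, 2.3, 5.4 and 6.1 agree on one binary primary outcome and 6.2.3 refers to a single primary logistic model. Section 5.4 supplies a 12-week window that could serve as a cut-off. The power figures rest on assumed rates, and the top of the range comes from one pair of medians with every patient starting. If 30% never start, the gaps are only about 2 to 10 points.

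Much of this stands. Cox regression as a secondary analysis is probably what was meant, the risk that status is chosen late is modest, and the large power losses belong to particular scenarios. It does not remove the defect. The one sentence that names a method for this outcome names logistic regression. The 12-week window is a length of follow-up, and no section turns it into a binary endpoint. An analyst should not have to infer the model by setting aside explicit text.

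**Conclusion.** The concern holds: 6.2.1 is wrong as written on both the method and the status of time to treatment initiation. Following it literally would leave unanswered whether treatment starts sooner. It would cost about 2 to 43 percentage points of power under the assumed exponential times and 12-week censoring. The loss depends on how many patients have started by week 12, and the upper end is inflated by the Wald test.

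The reach is limited to one secondary outcome of a pilot trial. The primary endpoint, its logistic analysis and the 124/138 sample size stand. It should be corrected before analysis.

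**What to change.** In 6.2.1, remove time to treatment initiation so that the primary analysis covers the binary endpoint only.

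In 6.2.2, name it as a secondary outcome: intention-to-treat, measured from randomization, Cox regression with arm as the covariate, hazard ratio with 95% confidence interval, censored at last contact or 12 weeks, whichever comes first. It is sensible to say in the same place that death before treatment is a competing event (cause-specific Cox model) and that cumulative-incidence curves will be shown by arm. The contradiction itself does not require that addition.

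If a binary version was intended, define it with its cut-off and state whether it is primary or secondary.

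The cost is about two sentences of plan wording. The same health-record dates are used, and data collection, sample size and primary power do not change.
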